**Table A. Characteristics of completed trials of transdermal glyceryl trinitrate.**

	GTN-1 30	GTN-2 31	GTN-3 24	RIGHT 28,32,33	ENOS 2,34-36	RIGHT-2 3,37-40
Setting	Hospital	Hospital	Hospital	Pre-hospital	Hospital	Pre-hospital
Time window (hr)	<120 hours	<72 hours	<120 hours	<4 hours	<48 hours	<4 hours
Stroke type	IS/ICH	IS/ICH	IS/ICH	IS/ICH	IS/ICH	IS/ICH
SBP range (mmHg)	No limits	100-230	140-220	>140	140-220	>120
Treatment blinding	Double-blind	Open-label	Single-blind	Single-blind	Single-blind	Single-blind
GTN dose (mg)	5	5/10	5	5	5	5
Thrombolysis given	N/A	N/A	N/A	After GTN	Before GTN	After GTN
Sample size						
Intended	38	90	18	80	>3500	850
Achieved	37	90	18	41	4011	1149

ICH: intracerebral haemorrhage; IS: ischaemic stroke; N/A: not applicable; SBP: systolic blood pressure

GTN lowered BP, increased heart rate, and did not alter cerebral blood flow (assessed using xenon CT) or platelet function. The safety and efficacy of GTN in patients with acute stroke (IS, ICH) has been assessed in two large phase III trials.

**International hospital-based MRC ENOS trial:** In comparison with no GTN, transdermal GTN was not associated with any difference in functional outcome (mRS), disability/Activities of Daily Living (BI), cognition (tMMSE, TICS, animal naming), mood (ZDS) or quality of life (EQ-5D/HUS, EQ-VAS) (Table B). No safety issues were found with GTN.

In the subgroup of patients randomised within 6 hours of ictus (average time from event to randomisation 263 minutes) (identified here as 'ENOS-early'), treatment with GTN was associated with reduced death, and improved functional outcome (mRS, BI) and quality of life (Table B)

**UK ambulance-based BHF RIGHT-2 trial:** The average time to treatment was 70 minutes. In comparison with sham, transdermal GTN was not associated with any differences in functional outcome (mRS), disability/Activities of Daily Living (BI), cognition (tMMSE, TICS, animal naming), mood (ZDS) or quality of life (EQ-5D/HUS, EQ-VAS).

**Table B. Outcomes in patients treated with GTN versus no GTN/sham**

Data are number (%), median [interquartile range] or mean (standard deviation). Analysis with binary logistic regression (odds ratio), ordinal logistic regression (odds ratio) or multiple regression (mean difference).

Outcome measure	GTN	No GTN	OR/MD (95% CI)	p
ENOS (OTR 0-48 hours) 				
Modified Rankin Scale (/6)	3 [3]	3 [3]	1.01 (0.91, 1.13)	0.83
Barthel Index (/100)	66 (38)	63 (39)	2.18 (-0.23, 4.59)	0.11
EQ-VAS (/100)	57 (31)	56 (32)	0.8 (-1.3, 2.9)	0.70
Death (%)	233 (12)	263 (13)	0.89 (0.72, 1.10)	0.27
ENOS-early (OTR 0-6 hours) 				
Modified Rankin Scale (/6)	3 [3]	3 [3]	0.53 (0.34, 0.82)	<0.001
Barthel Index (/100)	74 (34)	60 (41)	14 (4.6, 22.5)	0.01
EQ-VAS (/100)	62 (29)	53 (35)	9.6 (1.8, 17.5)	0.03
Death (%)	11 (8)	26 (20)	0.35 (0.13, 0.96)	0.04
RIGHT-2 (OTR 0-4 hours) 				
Modified Rankin Scale (/6)	3 [3]	3 [3]	1.25 (0.97, 1.60)	0.083
Barthel Index (/100)	56 (45)	58 (44)	-3 (-8, 2)	0.29
EQ-VAS (/100)	45 (34)	47 (32)	-0.9 (-5.1, 3.2)	0.66
Death (%)	97 (23)	79 (19)	1.24 (0.91, 1.86)	0.17

CI: confidence intervals; EQ-VAS: EuroQoL-Visual Analogue Scale; ICH: intracerebral haemorrhage; IS: ischaemic stroke; MD: mean difference; N/A: not applicable; OR: odds ratio; SBP: systolic blood pressure.

The following summary observations can be made based on data from the four phase II and two phase III GTN trials:

- Transdermal administration is advantageous since oral treatment is confounded by dysphagia in 50% of patients with acute stroke, whilst intravenous therapy requires intensive monitoring. Additionally, treatment can be stopped and restarted according to need.
- Peak concentrations of GTN are achieved by 1-2 hours.
- Transdermal GTN lowers systolic BP significantly by 15, 60 and 120 minutes.
- Transdermal GTN lowers central and peripheral SBP, DBP and pulse pressure; peak systolic BP and augmentation index; and 24-hour BP in both dipping and non-dipping patients.
- Transdermal GTN is feasible to administer, well tolerated, and safe when given early after acute stroke.
- GTN does not alter platelet function; hence, it can be given in ICH as well as IS.
- GTN does not reduce cerebral blood flow.
- GTN is safe in patients with severe carotid stenosis.

[figure not shown]
Further, the effect of GTN on functional outcome appears to be time-dependent when administered after stroke:

- <2.0 hours: No effect; indeed, GTN may cause harm in ICH in this ultra-acute period (interpretation from RIGHT-2 )
- 2.5 to 5.5 hours: May improve functional outcome (interpretation from ENOS-early  and meta-analysis, Figures A , B).

[figure not shown]
- >6 hours: No effect (interpretation from GTN 1/2/3 and ENOS and an individual patient data meta-analysis ).

(The positive effect of GTN on functional outcome in the phase II RIGHT trial is ignored here because it was small.)

**Figure A. Meta-analysis of GTN versus no GTN on end of trial functional outcome in patients treated within 6 hours of stroke onset (from )**

**Figure B. Meta-analysis of GTN versus no GTN on end of trial death in patients treated within 6 hours of stroke onset (from )**

In summary, GTN has been associated with beneficial effects on function and other clinical outcomes in hospitalised patients treated up to 6 hours after ictus. However, benefit was not seen in patients treated prior to hospital admission and there was weak evidence that ultra-acute treatment within 2 hours was associated with harm. As a result, ENOS-2 will assess, in a novel design, the feasibility of recruiting patients between 3 and 5 hours after ictus; if feasible, a larger safety and efficacy trial will be performed in this group of patients.

ENOS-2 will assess the feasibility, safety, and efficacy of hospital-delivered GTN when administered hyper-acutely after stroke. Five of the six GTN trials had a lower limit for systolic blood pressure of  $\geq 100$  mmHg,  $>120$  mmHg or  $\geq 140$  mmHg; the first study had no lower limit. Since several potential mechanisms by which GTN might work are BP-independent, ENOS-2 will follow the RIGHT-2 protocol and include patients with high-normal BP as well as high BP, with a lower limit set to  $\geq 120$  mmHg. This has the advantage that the results will apply to a wider population of stroke patients and include more patients with severe stroke (some of whom have SBP  $<140$  mmHg).

## **7 Objectives**

The purpose of the study is to determine whether it is feasible to recruit patients to transdermal glyceryl trinitrate (GTN) administered between 3-5-hours after the onset of stroke to inform a definitive trial.

### **7a Primary Objective:**

To assess the feasibility of recruiting, randomising, and treating patients with GTN vs sham and whether GTN lowers blood pressure.

### **7b Secondary Objectives:**

- i. To identify potential proof of concept on whether GTN reduces disability, low mood, poor cognition, and low quality of life.
- ii. Potential genetic markers include nitric oxide synthase polymorphisms, but others will be studied as relevant in searches of the scientific literature.
- iii. To investigate whether there is a difference in blood biomarkers between the two groups and whether biomarkers may be associated with outcome. Potential biomarkers include S-100 / nitric oxide (NOx) but others will be studied as relevant in searches of the scientific literature.

## **SECTION 3. STUDY METHODS**

### **8 Trial design**

ENOS-2 is a prospective parallel-group randomised sham-controlled masked-endpoint phase II feasibility and safety trial of GTN versus sham with randomisation between 3 and 5 hours after stroke.

### **9 Sample size/power considerations**

ENOS-2 is a feasibility study hence there is no formal sample size calculation. However, recruitment of 100 participants would allow an adjusted common odds ratio, acOR 0.51 to be detected, assuming mRS distribution as in; alpha 0.05, power 0.80. The number of targeted participants will be 100 with ischaemic stroke (50 randomised to GTN, 50 randomised to sham) and 20 with intracerebral haemorrhage for safety (10 randomised to GTN, 10 randomised to sham).

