**Table 2. Outcomes in patients treated with GTN versus no GTN/sham**

Data are number (%), median [interquartile range] or mean (standard deviation). Analysis with binary logistic regression (odds ratio), ordinal logistic regression (odds ratio) or multiple regression (mean difference).

Outcome measure	GTN	No GTN	OR/MD (95% CI)	p
ENOS (OTR 0-48 hours) 				
Modified Rankin Scale (/6)	3 [3]	3 [3]	1.01 (0.91, 1.13)	0.83
Barthel Index (/100)	66 (38)	63 (39)	2.18 (-0.23, 4.59)	0.11
EQ-VAS (/100)	57 (31)	56 (32)	0.8 (-1.3, 2.9)	0.70
Death (%)	233 (12)	263 (13)	0.89 (0.72, 1.10)	0.27
ENOS-early (OTR 0-6 hours) 				
Modified Rankin Scale (/6)	3 [3]	3 [3]	0.53 (0.34, 0.82)	<0.001
Barthel Index (/100)	74 (34)	60 (41)	14 (4.6, 22.5)	0.01
EQ-VAS (/100)	62 (29)	53 (35)	9.6 (1.8, 17.5)	0.03
Death (%)	11 (8)	26 (20)	0.35 (0.13, 0.96)	0.04
RIGHT-2 (OTR 0-4 hours) 				
Modified Rankin Scale (/6)	3 [3]	3 [3]	1.25 (0.97, 1.60)	0.083
Barthel Index (/100)	56 (45)	58 (44)	-3 (-8, 2)	0.29
EQ-VAS (/100)	45 (34)	47 (32)	-0.9 (-5.1, 3.2)	0.66
Death (%)	97 (23)	79 (19)	1.24 (0.91, 1.86)	0.17

CI: confidence intervals; EQ-VAS: EuroQoL-Visual Analogue Scale; ICH: intracerebral haemorrhage; IS: ischaemic stroke; MD: mean difference; N/A: not applicable; OR: odds ratio; SBP: systolic blood pressure.

The following summary observations can be made based on data from the four phase II and two phase III GTN trials:

[figure not shown]
- Transdermal administration is advantageous since oral treatment is confounded by dysphagia in 50% of patients with acute stroke, whilst intravenous therapy requires intensive monitoring. Additionally, treatment can be stopped and restarted according to need.
- Peak concentrations of GTN are achieved by 1-2 hours.
- Transdermal GTN lowers systolic BP significantly by 15, 60 and 120 minutes.
- Transdermal GTN lowers central and peripheral SBP, DBP and pulse pressure; peak systolic BP and augmentation index; and 24-hour BP in both dipping and non-dipping patients.
- Transdermal GTN is feasible to administer, well tolerated, and safe when given early after acute stroke.
- GTN does not alter platelet function; hence, it can be given in ICH as well as IS.
- GTN does not reduce cerebral blood flow.

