### **11 Randomisation**

Patients will be randomised 1:1 to receive either 5 mg transdermal GTN versus sham transdermal DuoDERM hydrocolloid dressing placed on the back or shoulders for two days. Randomisation will be performed by the Stroke Trials Unit (STU) in Nottingham and involve computerised stratification by stroke type (IS or not known; ICH) and minimisation on age, severity, time, systolic blood pressure and candidate for or received reperfusion therapy. Patients, relatives, researchers, and outcome assessors will be masked to treatment allocation.

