#### ***15b Confidence intervals***

The results of analyses and comparisons will be shown with 95% confidence intervals.

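### The stated 80% power for a common odds ratio of 0.51 with 100 participants is wrong: power is just under 50%, and the odds ratio detectable at 80% power is about 0.37

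*SAP*

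**What the plan says.** Section 9 of the SAP says that a feasibility study needs no formal sample size calculation, then adds that "recruitment of 100 participants would allow an adjusted common odds ratio, acOR 0.51 to be detected", with "alpha 0.05, power 0.80" and the mRS distribution of the cited early-treatment subgroup of the earlier ENOS trial. The same sentence stands in the Protocol Synopsis under the sample size estimate.

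The target in SAP section 9 is "100 with ischaemic stroke (50 randomised to GTN, 50 randomised to sham"), plus "20 with intracerebral haemorrhage for safety (10 randomised to GTN, 10 randomised to sham"). SAP section 11 confirms equal allocation: "Patients will be randomised 1:1".

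Neither document says whether alpha is one- or two-sided, lists the mRS category proportions, or states a gain from covariate adjustment. SAP section 15b points to two-sided inference: "The results of analyses and comparisons will be shown with 95% confidence intervals". SAP section 25d adjusts for the minimisation covariates, and section 27 rules out imputation.

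**The concern.** An odds ratio of 0.51 is close to the early-subgroup result in Protocol Table 2, "0.53 (0.34, 0.82"). That result came from a subgroup of roughly 256 to 280 patients, and its upper limit is only moderately below 1. A trial of 100 would be expected to have much less than 80% power for an effect of that size.

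The mRS is the primary clinical outcome. SAP Table 3 reports it with an adjusted odds ratio, confidence interval and p value, and the secondary objectives look for efficacy signals or proof of concept to inform a definitive trial. A reader who accepts 80% power for 0.51 could take a neutral mRS result as evidence against an effect as large as the one that motivated the trial. In fact the trial would miss that effect more often than not.

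**Working it through.** **Inputs**

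- Odds ratio 0.51, alpha 0.05, power 0.80, N = 100 as 50 + 50, 1:1 allocation (SAP sections 9 and 11). ln 0.51 = −0.6733, squared 0.4534.
- Seven mRS levels, 0 to 6 (SAP Table C, note 6).
- Two-sided alpha, taken from SAP section 15b: z = 1.960; for 80% power z = 0.842; sum 2.802, squared 7.849.
- mRS proportions: not in the documents, so handled by a bound and by assumed distributions.

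**Formula (proportional odds, equal allocation)**

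N = 12(zα + zβ)² / [(ln OR)² (1 − Σp̄ᵢ³)], where p̄ᵢ is the proportion in category i averaged over the arms.

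**Attempt to reproduce the plan's figure, best case**

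The distribution enters only through 1 − Σp̄ᵢ³. With seven categories this is largest when all are equal: 1 − 7(1/7)³ = 48/49 = 0.9796. Hence, for any seven-level distribution:

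- N for 80% power at 0.51 is at least 12 × 7.849 / (0.4534 × 0.9796) = 212, against 100 stated.
- Power at N = 100 is at most Φ(√(100 × 0.4534 × 0.9796 / 12) − 1.960) = Φ(1.924 − 1.960) = 0.486, against 0.80 stated.
- The odds ratio detectable at 80% power with N = 100 is at best exp(−2.802 × √(12 / (100 × 0.9796))) = exp(−2.802 × 0.350) = 0.375.

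**Assumed distributions**

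Four control-arm distributions were tried, each with 20% deaths and median mRS 3 as in the early subgroup of Table 2. They ranged from well spread to 45% in one category.

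| Quantity | Range |
|---|---|
| 1 − Σp̄³ | 0.899 to 0.977 |
| Power at N = 100 | 0.453 to 0.485 |
| Detectable odds ratio at N = 100 | 0.359 to 0.375 |
| N for 80% power at 0.51 | 213 to 231 |

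**Other readings of the sentence** (range over the assumed distributions and the equal-category best case)

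| Reading | Power for 0.51 |
|---|---|
| All 120 participants | 0.52 to 0.56 |
| One-sided alpha 0.05 (N needed 167 to 182) | 0.58 to 0.61 |
| Two-sided, assumed 30% saving in N from adjustment (N needed 148 to 162) | 0.60 to 0.63 |
| One-sided and 30% saving | 0.71 to 0.74 |
| mRS dichotomised (control proportion 50% to 65%) | 0.37 to 0.38 |
| 200 participants (100 per arm) | 0.74 to 0.78 |

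None reaches 0.80. For 100 to suffice, adjustment would have to cut the required N by 53% to 57% (1 − 100/212 to 1 − 100/231).

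**Simulation**

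- Mann-Whitney test, 50 per arm, 5,000 runs per setting: power 0.43 to 0.49.
- Adjusted proportional-odds model with a prognostic covariate and a conditional odds ratio of 0.51, 400 runs per setting: 0.39 to 0.48. A second set, 600 runs per setting: 0.46 to 0.49. Monte Carlo standard error is about 0.02 to 0.025.

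Adjustment does not help here because 0.51 is already specified as the adjusted odds ratio.

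**Cross-check from Table 2**

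From the interval 0.34 to 0.82, SE(log OR) = ln(0.82/0.34)/3.92 = 0.2246. Deaths of 11 (8%) and 26 (20%) imply about 256 to 280 patients, allowing for rounding. Scaled to 100 patients, SE = 0.2246 × √2.56 to 0.2246 × √2.80 = 0.359 to 0.376. Power for 0.51 is then 0.43 to 0.47 and the detectable odds ratio 0.35 to 0.365.

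**At the progression threshold**

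The best-case formula gives power of at most 0.36 at 70 participants (Synopsis; SAP section 25b) and 0.38 at 75 (Protocol Statistics section).

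**The case against.** The strongest reply is that the sentence is an aside. Both documents disclaim a formal calculation, the Protocol plans no formal assessment of efficacy, the comparisons are exploratory, and progression depends on recruitment, compliance and follow-up. Confidence intervals will show the imprecision, and the definitive trial will have its own calculation. All of this is true: no patient number, analysis or decision rule depends on the figure. It limits the consequences of the error but does not make the figure correct.

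Three narrower objections also have force:

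- **The Table 2 cross-check is soft.** The table does not say that 0.53 is adjusted, the denominators are back-calculated from rounded percentages, and the row prints p < 0.001 although its interval implies p of about 0.005. If the p value were right and the interval wrong, the SE would be below 0.193; at 0.193, scaled power is 0.55 to 0.59 and the N needed 165 to 180. That is still well short of the claim, and the formula bound does not use this row.
- **The origin of the error is unknown.** About 100 per arm would detect roughly 0.50, so a per-arm number may have been quoted as a total. The documents cannot confirm this, and 100 per arm gives at most 0.78 power.
- **The exact replacement figure depends on the cited mRS distribution**, which is not in the documents, and on the number analysed. The ceiling of 48.6% does not depend on the distribution.

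**Conclusion.** The concern holds. With 100 participants in two equal arms and two-sided alpha 0.05, formula power for a common odds ratio of 0.51 is 45% to 48% under plausible mRS distributions and cannot exceed 48.6% under any seven-level distribution; the plan states 80%. The odds ratio detectable at 80% power is about 0.36 to 0.37, and no closer to 1 than 0.375. The stated effect needs at least 212 participants, more than twice the number given.

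This rests on proportional odds, complete mRS data and two-sided testing. One-sided testing raises power only to about 61%. Because missing data are not imputed, any loss to follow-up lowers power further.

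**What to change.** Keep the sample size and correct the sentence in SAP section 9 and the Protocol Synopsis. Suggested wording: *With 100 participants (50 per arm), two-sided alpha 0.05 and 80% power, the smallest effect detectable is a common odds ratio of about 0.37; power for an odds ratio of 0.51 is just under 50%.*

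The sponsor should first recompute both figures from the mRS proportions in the cited subgroup paper, and state the number analysed, the sidedness and any adjustment gain assumed. If a power figure is not wanted in a feasibility trial, deleting the sentence from both documents is equally sound.

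The cost is one sentence in each document and a less favourable figure. No extra participants and no change to the analyses are needed.

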- GTN is safe in patients with severe carotid stenosis.

Further, the effect of GTN on functional outcome appears to be time-dependent when administered after stroke:

[figure not shown]
- <2.0 hours: No effect; indeed, GTN may cause harm in ICH in this ultra-acute period (interpretation from RIGHT-2 )
- 2.5 to 5.5 hours: May improve functional outcome (interpretation from ENOS-early  and meta-analysis, Figures 1 , 2).
- >6 hours: No effect (interpretation from GTN 1/2/3 and ENOS and an individual patient data meta-analysis ).

(The positive effect of GTN on functional outcome in the phase II RIGHT trial is ignored here because it was small.)

**Figure 1. Meta-analysis of GTN versus no GTN on end of trial functional outcome in patients treated within 6 hours of stroke onset (from )**

**Figure 2. Meta-analysis of GTN versus no GTN on end of trial death in patients treated within 6 hours of stroke onset (from )**

In summary, GTN has been associated with beneficial effects on function and other clinical outcomes in hospitalised patients treated up to 6 hours after ictus. However, benefit was not seen in patients treated prior to hospital admission and there was weak evidence that ultra-acute treatment within 2 hours was associated with harm. As a result, ENOS-2 will assess, in a novel design, the feasibility of recruiting patients between 3 and 5 hours after ictus; if feasible, a larger safety and efficacy trial will be performed in this group of patients.

ENOS-2 will assess the feasibility, safety, and efficacy of hospital-delivered GTN when administered hyper-acutely after stroke. Five of the six GTN trials had a lower limit for systolic blood pressure of  $\geq 100$  mmHg,  $>120$  mmHg or  $\geq 140$  mmHg, the first study had no lower limit. Since several potential mechanisms by which GTN might work are BP-independent, ENOS-2 will follow the RIGHT-2 protocol and include patients with high-normal BP as well as high BP, with a lower limit set to  $\geq 120$  mmHg. This has the advantage that the results will apply to a wider population of stroke patients and include more patients with severe stroke (some of whom have SBP  $<140$  mmHg).

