### **12 Statistical interim analyses and stopping guidance.**

#### **12a Interim analyses:**

An independent Data Monitoring Committee (DMC) will be established. The DMC will receive safety reports twice yearly, or more if requested, and perform unblind reviews of safety and efficacy data. The DMC have responsibility to monitor SAEs and neurological deterioration and outcome in IS and ICH separately. No interim analysis will be performed.

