## **SECTION 6. ANALYSIS**

### **24 Outcome definitions**

#### ***24a Primary endpoint***

The primary end point of the study is the feasibility of recruiting and treating 120 patients (100 IS, 20 ICH) between 3 and 5 hours after stroke.

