### **26 Subgroup analyses:**

The primary clinical outcome will be analysed in subgroups consisting of the minimisation factors:

- Age (years):  $\leq 70$ ,  $> 70$
- Stroke severity, NIHSS (/42):  $\leq 10$ ,  $> 10$
- Time after stroke (minutes):  $\leq 220$ ,  $> 220$
- Systolic blood pressure (mmHg):  $\leq 160$ ,  $> 160$
- Received reperfusion therapy: yes, no

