**Table 9. Participants with at least one serious adverse event by organ randomised to GTN versus Sham control.**

Data are number (%), and comparison by binary logistic regression.

	All			Fatal		
	GTN	Control	Difference (p)	GTN	Control	Difference (p)
Number						
Cardiovascular	xxx (xxx)	xxx (xxx)	xxx (xxx, xxx), p=0.xxx	xxx (xxx)	xxx (xxx)	xxx (xxx, xxx), p=0.xxx
Hypotension	xxx (xxx)	xxx (xxx)	xxx (xxx, xxx), p=0.xxx	xxx (xxx)	xxx (xxx)	xxx (xxx, xxx), p=0.xxx
Nervous system	xxx (xxx)	xxx (xxx)	xxx (xxx, xxx), p=0.xxx	xxx (xxx)	xxx (xxx)	xxx (xxx, xxx), p=0.xxx
Haemorrhagic transformation	xxx (xxx)	xxx (xxx)	xxx (xxx, xxx), p=0.xxx	xxx (xxx)	xxx (xxx)	xxx (xxx, xxx), p=0.xxx
Transient ischaemic attack	xxx (xxx)	xxx (xxx)	xxx (xxx, xxx), p=0.xxx	xxx (xxx)	xxx (xxx)	xxx (xxx, xxx), p=0.xxx
Respiratory	xxx (xxx)	xxx (xxx)	xxx (xxx, xxx), p=0.xxx	xxx (xxx)	xxx (xxx)	xxx (xxx, xxx), p=0.xxx
Gastrointestinal	xxx (xxx)	xxx (xxx)	xxx (xxx, xxx), p=0.xxx	xxx (xxx)	xxx (xxx)	xxx (xxx, xxx), p=0.xxx
Genitourinary	xxx (xxx)	xxx (xxx)	xxx (xxx, xxx), p=0.xxx	xxx (xxx)	xxx (xxx)	xxx (xxx, xxx), p=0.xxx
Haematological/immunological	xxx (xxx)	xxx (xxx)	xxx (xxx, xxx), p=0.xxx	xxx (xxx)	xxx (xxx)	xxx (xxx, xxx), p=0.xxx
Metabolic/endocrine	xxx (xxx)	xxx (xxx)	xxx (xxx, xxx), p=0.xxx	xxx (xxx)	xxx (xxx)	xxx (xxx, xxx), p=0.xxx
Musculoskeletal/cutaneous	xxx (xxx)	xxx (xxx)	xxx (xxx, xxx), p=0.xxx	xxx (xxx)	xxx (xxx)	xxx (xxx, xxx), p=0.xxx
Miscellaneous	xxx (xxx)	xxx (xxx)	xxx (xxx, xxx), p=0.xxx	xxx (xxx)	xxx (xxx)	xxx (xxx, xxx), p=0.xxx
Other	xxx (xxx)	xxx (xxx)	xxx (xxx, xxx), p=0.xxx	xxx (xxx)	xxx (xxx)	xxx (xxx, xxx), p=0.xxx
Total	xxx (xxx)	xxx (xxx)	xxx (xxx, xxx), p=0.xxx	xxx (xxx)	xxx (xxx)	xxx (xxx, xxx), p=0.xxx

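### Twenty ICH patients are recruited for safety, but no final outcome or SAE table is split by stroke type; a descriptive IS/ICH breakdown should be added

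*SAP*

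**What the plan says.** SAP 9 gives two targets. The first is "100 with ischaemic stroke (50 randomised to GTN, 50 randomised to sham". The second, the only one with a stated purpose, is "20 with intracerebral haemorrhage for safety (10 randomised to GTN, 10 randomised to sham". The primary endpoint in SAP 24a is the "feasibility of recruiting and treating 120 patients (100 IS, 20 ICH) between 3 and 5 hours after stroke".

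The design treats stroke type as important. It stratifies randomisation, in two strata: IS or not known, and ICH (SAP 11). During the trial, "The DMC have responsibility to monitor SAEs and neurological deterioration and outcome in IS and ICH separately" (SAP 12a; the protocol's section on stopping rules says the same).

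The final analysis is set out differently:

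- **Subgroups (SAP 26):** "The primary clinical outcome will be analysed in subgroups consisting of the minimisation factors". These are age, NIHSS, time, systolic blood pressure and reperfusion. Stroke type is the stratification factor, so this rule leaves it out.
- **Covariates (SAP 25d):** the same five factors, without stroke type.
- **Outcome and SAE tables:** Tables 3, 4 and 8 compare GTN with sham in all patients. Table 9 is titled "Participants with at least one serious adverse event by organ randomised to GTN versus Sham control". None is split by stroke type.
- **Where ICH does appear:** recruitment counts in Table 2; primary ICH as a scan result in Table 1 and as a final diagnosis in Table 6; and the event rows for symptomatic ICH and ICH expansion in Table 4.

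**The concern.** The ICH patients are the only group recruited for a stated safety purpose, yet no planned final table gives their deaths, SAEs, hypotension, neurological deterioration or mRS by arm. They are to be 10 of 60 patients per arm, so every pooled safety figure is driven by IS. An excess confined to ICH could be present in the data and barely show in the report.

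The trial is meant to inform a definitive trial, whose designers will have to consider whether to include ICH. They would have no ICH safety result to look at. If someone then asked for the breakdown after unblinding, it would be post hoc, although stroke type was important enough to stratify on.

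**Working it through.** **Inputs from the documents.** ICH: 10 GTN, 10 sham. IS: 50 GTN, 50 sham (SAP 9). Total 10 + 50 = 60 per arm, 120 in all, which agrees with SAP 24a. No calculation supports the 20 ICH patients. The one detectable-effect statement in SAP 9 concerns mRS in 100 participants and is not used here.

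**Inputs not in the documents.** Event risks by stroke type are not given, so those below are assumptions.

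**Step 1: dilution.** With the same ICH share w in both arms,

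pooled RD = w × RD(ICH) + (1 − w) × RD(IS).

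At target, w = 10/60 = 1/6. If RD(IS) = 0, the pooled RD is RD(ICH)/6, whatever the event risks.

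**Step 2: illustration.** Assume ICH 20% (sham) v 50% (GTN), and IS 10% in both arms.

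- Sham: (50 × 0.10 + 10 × 0.20)/60 = 7/60 = 11.7%
- GTN: (50 × 0.10 + 10 × 0.50)/60 = 10/60 = 16.7%
- Difference: 3/60 = 5 points, against 30 points within ICH
- Odds ratio: (0.5/0.5)/(0.2/0.8) = 4.0 within ICH; (10/50)/(7/53) = 1.5 pooled

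The factor of one sixth therefore applies to the risk difference and not to the odds ratio, which is what the planned logistic regressions report.

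**Step 3: range.** Keep a 30-point ICH excess, vary the sham ICH risk, and take 12% in IS in both arms (the all-stroke death percentage in the ENOS GTN arm, used as a stand-in). Power is for a two-sided 5% Fisher test, treating pooled counts as binomial.

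| ICH sham v GTN | Pooled risks | Pooled RD | Power, ICH alone (10 v 10) | Power, pooled (60 v 60) |
|---|---|---|---|---|
| 10% v 40% | 11.7% v 16.7% | 5 points | 0.15 | 0.08 |
| 20% v 50% | 13.3% v 18.3% | 5 points | 0.13 | 0.07 |
| 30% v 60% | 15.0% v 20.0% | 5 points | 0.12 | 0.07 |

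Pooling hides the size of the difference, but power is low either way. The small ICH number is the main reason.

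**Step 4: what 10 per arm can show.**

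- Exact (Clopper-Pearson) 95% limits: for 0/10, the upper limit is 1 − 0.025^(1/10) = 0.308, so 0% to 31%; for 2/10, 3% to 56%.
- Smallest splits with Fisher p ≤ 0.05: 0/10 v 5/10 (p = 0.033) and 1/10 v 7/10 (p = 0.020).
- From 20% on sham, 80% power needs about 88% on GTN.

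**The case against.** The strongest reply is that ICH safety is already looked at separately. The DMC reviews unblinded data twice yearly and monitors SAEs, deterioration and outcome by stroke type. A reader might infer from the tables that the trial plans no ICH-specific safety comparison at all; SAP 12a shows that this is wrong. The gap is in final reporting. It remains, because the protocol's DMC section says that the committee will not give specific unmasked results to the TSC or the Chief Investigator, and SAP 12c has no formal stopping rules.

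Second, it would be too broad to say that ICH is absent from the tables. Tables 1, 2, 4 and 6 have ICH rows, and ICH expansion is a direct measure of harm. But that row sits in a table headed by all patients randomised, with no ICH-only denominator stated, although only ICH patients can have the event.

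Third, a split would not answer the ICH question. This stands: steps 3 and 4 show that 10 v 10 gives counts and wide intervals, and no stated objective is specific to ICH.

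Fourth, the protocol background does say that "GTN may cause harm in ICH in this ultra-acute period", but of treatment before 2.0 hours. The same list says that treatment at 2.5 to 5.5 hours may improve function. The documents do not flag ICH harm in the trial's own 3-5 hour window.

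Finally, SAP 9 says that "recruitment of 100 participants would allow an adjusted common odds ratio, acOR 0.51 to be detected", and 100 is also the IS target. A reader might infer that an IS-only mRS analysis was intended and dropped. The text says participants, not IS patients, and the mRS distribution comes from an ENOS subgroup, a trial that enrolled both types. The inference is not supported.

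**Conclusion.** The point holds as a gap in the final reported analysis. The plan recruits, stratifies and monitors by stroke type, then reports outcomes and SAEs pooled. On the risk-difference scale, an effect confined to ICH appears at one sixth of its size, provided that targets are met, arms are balanced and there is no IS effect. Balance at 10 v 10 is not guaranteed, because an unscanned ICH patient can be randomised in the IS or not-known stratum. The 30-to-5-point example rests on assumed risks; the factor of one sixth does not.

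This should be fixed, but it does not threaten the trial's main conclusion: the primary endpoint is feasibility, and between-group comparisons are exploratory (SAP 25c). The omission withholds information and biases no primary result.

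**What to change.** Before database lock and release of the randomisation codes:

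1. **SAP 26 and 25d:** add stroke type to the subgroups and to the covariates. In SAP 26, show the mRS distribution by arm within type, and do not rely on a treatment-by-type interaction test with about 10 ICH patients per arm.
2. **Tables 3, 4, 8 and 9:** add IS and ICH panels by confirmed final diagnosis (already recorded for Table 6), and count the remaining diagnoses so that the totals agree. Across these tables, give death, neurological deterioration, hypotension, any SAE and the mRS distribution by arm. Show event outcomes as n/N with exact 95% intervals.
3. **Table 4, ICH expansion:** use ICH patients only as the denominator. The symptomatic ICH row should not be restricted in this way, because haemorrhagic transformation occurs in IS.
4. **Statement in the SAP:** the ICH panels are descriptive, and an absence of events in about 10 patients per arm is not evidence of safety.

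The cost is some SAP wording and a few table panels from data already collected. The intervals will be wide, and the report should say so.
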